5.2.6 Medical History

Prior to enrollment, subjects will be assessed for pre-existing conditions and illnesses, both past and ongoing. Any such conditions will be documented in the source document. Significant (clinically relevant) medical history (reported as diagnosis) including conditions/illnesses for which the subject is or has been followed by a physician or conditions/illnesses that could resume during the course of the study or lead to an SAE or to a repetitive outpatient care will be collected in the case report book (CRB). The significant medical history section of the CRB contains a core list of body systems and disorders that could be used to prompt comprehensive reporting, as well as space for the reporting of specific conditions and illnesses.

For each condition, the data collected will be at least:

- Diagnosis (this is preferable to reporting signs and symptoms)
- Presence or absence of the condition at enrollment

The reporting of signs and symptoms in lieu of a diagnosis is strongly discouraged.

Dates, medications, and body systems are not to be recorded, and the information collected will not be coded. Its purpose is to assist in the later interpretation of safety data collected during the study. Given the current COVID-19 pandemic, the medical history must actively include if suspected/confirmed COVID-19 happened, dates, treatments received and dosages. The use of medications (prescribed or out-of-the-counter) such as chloroquine and hydroxychloroquine within at least 2 months before enrollment should be recorded, given their interference with rabies vaccines (22) (27).

^a Chronic illness may include, but is not limited to, neurological, cardiopulmonary, gastrointestinal, renal, genitourinary, metabolic, hematologic, auto-immune, or psychiatric disorders or infection.

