6.9 Concomitant Medications and Other Therapies

At the time of enrollment, ongoing medications and other therapies (eg, blood products) should be recorded in the source document as well as new medications prescribed for new medical conditions / AEs during study participation.

Documentation in the CRB of ongoing concomitant medication(s) will be limited to specific categories of medication(s) of interest beginning on the day of the first vaccination. This may include medications of interest that were started prior to the day of vaccination.

Reportable medications will be collected in the CRB from the day of each vaccination to the end of the solicited and unsolicited follow-up period (ie, from V01 to V07) as they may impact the response to the vaccination and impact the consistency of the information collected on concomitant medications at any vaccination.

Reportable medications include medications that impact or may impact the consistency of the safety information collected after any vaccination and/or the immune response to vaccination. Three standard categories of reportable medications are defined:

- Category 1: medications impacting or that may have an impact on the evaluation of the safety (eg, antipyretics, analgesics, and non-steroidal anti-inflammatory drugs [NSAIDs], steroids/corticosteroids and other immune modulators).
- Category 2: medications impacting or that may have an impact on the immune response (eg, other vaccines, blood products, antibiotic classes that may interfere with bioassays used by the GCI department, steroids/corticosteroids, immune-suppressors, immune modulators with immunosuppressive properties, anti-proliferative drugs such as DNA synthesis inhibitors).
- Category 3: medications impacting or that may have an impact on both the safety and the immune response (eg, steroids/corticosteroids)

Medications should be collected as concomitant if there is a reasonable possibility that they may still impact on safety and/or immune assessment, even when the treatment was stopped before collection (e.g. medications characterized by long half-life, dose accumulation, or which might cause delayed adverse reactions).

Additionally, given the COVID-19 pandemic and the possible use of medications with or without medical prescription, medications that interfere with the immune response should be actively evaluated. For instance, chloroquine or hydroxychloroquine received within at least 2 months

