12.1.3 Exploratory analyses

With the aim to provide the same standards and granularity in terms of investigational results across VRVg studies, and comply with health authorities requirements (33), the possible influence of several covariates on the safety and immunogenicity results will be studied using descriptive statistics. Thus, the main immunogenicity and safety parameters will be described according to gender, age, ethnicity (only if more than 5% of subjects had different ethnicity), race (only if more than 5% of subjects had different race), and center. Race and ethnicity will be defined according to current guidelines (33).

The possible impact of the COVID-19 pandemic on the immunogenicity and safety results will be assessed and corresponding exploratory analyses will be detailed in the Statistical Analysis Plan.

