4.1.3.2 Impact of the COVID-19 pandemic

To evaluate the possible impact of the COVID-19 pandemic on the study conduction, main immunogenicity and safety results, the following sensitive analyses will be performed but not limited to:

- Impact of COVID-19 pandemic on subject's disposition, based on enrolled subjects
Note: Subjects impacted by COVID-19 pandemic situation correspond to subjects with at least one major/critical protocol deviation due to COVID-19 or who did not complete the study due to COVID-19 or who reported an impact on 6-month follow up in pandemic form
- Impact of COVID-19 pandemic on immunogenicity analysis, based on FASI.
- Impact of medical history of suspected/confirmed COVID-19 pandemic before enrollment on immunogenicity analysis, based on FASI.
- Impact of the use of concomitant medications that are used during the study/ or were used not over 2 months before enrollment for treating/preventing COVID-19 (ie, Hydroxychloroquine and chloroquine) on immunogenicity based on FASI.
- Immunogenicity of subjects who did not take any concomitant medications for treating/preventing COVID-19 (ie, Hydroxychloroquine and chloroquine) within 2 months before enrollment based on PPAS
- Impact of COVID-19 pandemic on safety overview up to 28 days after any vaccination, based on SafAS.
- Impact of medical history of suspected/confirmed COVID-19 before enrollment on safety overview up to 28 days after any vaccination, based on SafAS.
- Impact of the use of concomitant medications that are used during the study/ or were used at least 2 months before enrollment for treating/preventing COVID-19 (ie, Hydroxychloroquine and chloroquine) on safety overview up to 28 days after any vaccination, based on SafAS.

Note: If only few subjects were impacted by COVID-19 (<5% in randomized subjects), only the corresponding listings will be provided instead of tables for immunogenicity and safety evaluation. Exception is the immunogenicity evaluation for the subjects who did not take any concomitant

medications for treating/preventing COVID-19 (ie, Hydroxychloroquine and chloroquine) within 2 months before enrollment base on PPAS.

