4.2.5 Populations Used in Analyses

The following table presents populations used in the statistical analysis.

Table 4.5: Populations used in the analyses

		Analysis sets	Analysis by
Primary Objective	D28 non-inferiority testing	PPAS (main analysis), FAS/FASI	Received vaccine group Randomized vaccine group
Secondary Objectives	D28 Superiority testing	PPAS (main analysis), FAS/FASI	Received vaccine group Randomized vaccine group
	Immunogenicity description	PPAS (main analysis), FAS/FASI	Received vaccine group Randomized vaccine group
	Safety description	SafAS	Received vaccine group
Exploratory analyses	Main immunogenicity endpoints	FASI (main analysis) PPAS*	Randomized vaccine group Received vaccine group
	Main safety endpoints	SafAS	Received vaccine group

*Note: Immunogenicity of subjects who did not take any concomitant medications for treating/preventing COVID-19 (ie, Hydroxychloroquine and chloroquine) within 2 months before enrollment

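### SAP 4.1.3.2 selects chloroquine/hydroxychloroquine users by use in the last 2 months for immunogenicity, but by use 2 months or more before enrollment for safety

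*SAP*

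**What the plan says.** Protocol section 12.1.3 announces an assessment of the pandemic's impact and says that the "corresponding exploratory analyses will be detailed in the Statistical Analysis Plan". SAP section 4.1.3.2 supplies the detail. Three of its analyses depend on when chloroquine or hydroxychloroquine was taken before enrollment:

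- **Immunogenicity in users (FASI):** use during the study, or drugs that "were used not over 2 months before enrollment for treating/preventing COVID-19".
- **Immunogenicity in non-users (PPAS):** subjects with no such use "within 2 months before enrollment based on PPAS". The exception note at the end of the section repeats the window ("within 2 months before enrollment base on PPAS"), and so does the footnote to Table 4.5 in SAP section 4.2.5: "Immunogenicity of subjects who did not take any concomitant medications for treating/preventing COVID-19 (ie, Hydroxychloroquine and chloroquine) within 2 months before enrollment".
- **Safety overview in users (SafAS):** "Impact of the use of concomitant medications that are used during the study/ or were used at least 2 months before enrollment".

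On the collection side, Protocol section 5.2.6 asks that use of these drugs "within at least 2 months before enrollment should be recorded, given their interference with rabies vaccines". Section 6.9 has similar wording for concomitant medication: "For instance, chloroquine or hydroxychloroquine received within at least 2 months". Section 6.9 also has start and stop dates entered for each reported medication.

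**The concern.** The two user analyses are worded in parallel and concern the same two drugs, yet their pre-enrollment windows run in opposite directions. The SAP gives no reason for a different window in the safety analysis. A programmer following the text would build two different exposure flags. Subjects who took the drug only shortly before enrollment would count as users for immunogenicity but not for safety. Subjects who took it only in the more distant past would count the other way round. The two results would be read side by side as describing users of the same drugs, although they select different people for a reason unrelated to the FASI/SafAS difference. If users are set against non-users, recent users would sit on the non-user side of the safety comparison.

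**Working it through.** There is no sample size, power or error-rate figure to reproduce. The check sets the window statements side by side and then applies the two user rules to each possible pattern of use.

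**Step 1. The SAP's statements of the window**

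| Place in the SAP | Analysis | Window before enrollment |
|---|---|---|
| 4.1.3.2, FASI item | immunogenicity in users | 2 months or less |
| 4.1.3.2, PPAS item | immunogenicity in non-users | 2 months or less |
| 4.1.3.2, exception note | same PPAS analysis | 2 months or less |
| 4.2.5, Table 4.5 footnote | same PPAS analysis | 2 months or less |
| 4.1.3.2, SafAS item | safety in users | 2 months or more |

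Four statements agree and one conflicts. Three of the four restate a single analysis, so by distinct analysis the count is two against one. The SafAS item is the odd one out on either count.

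**Step 2. Who is selected**

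Let *t* be the time in months from a given use back from enrollment. The FASI rule takes pre-enrollment use with *t* ≤ 2. The literal SafAS rule takes *t* ≥ 2. They share only *t* = 2. Counting a subject as a user if any use falls in the window:

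| Pattern of use | FASI rule | Literal SafAS rule |
|---|---|---|
| Use during the study | selected | selected |
| Only in the last 2 months (e.g. 1 month before) | selected | not selected |
| Only earlier (e.g. 4 months before) | not selected | selected |
| Before enrollment only, spanning the 2-month point | selected | selected |

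The 1 and 4 months are illustrations, not figures from the documents. Two of the three pre-enrollment-only patterns are classified differently. If *t* were instead measured from the last use, a subject whose use spanned the 2-month point would have *t* < 2 and would also be discordant, making three of three. The SAP does not say which is meant, but the conflict is present under both.

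**Step 3. Whether the protocol resolves it**

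It does not. Section 12.1.3 leaves the detail to the SAP. The wording in sections 5.2.6 and 6.9 asks for a look-back covering at least the most recent 2 months and sets no upper limit. Under that requirement use in the last 2 months must be recorded, while earlier use need not be. The literal safety rule therefore selects on the period in which recording is least assured and leaves out the period in which it is required. A plausible origin, which is an inference, is that the safety item shortened the protocol's phrase and lost the word *within*, which reverses its meaning.

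**The case against.** The strongest reply is that this is a dropped word and not a design decision. Read as a shortened form of the protocol's look-back, the safety item would include recent users and merely fail to cap the window. Nothing in the documents shows that the literal version was programmed. That is fair as an account of intent, but the text as it stands does not say so, and the documents do not show which rule was used.

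Several limits on the consequence also stand:

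- The four agreeing statements cover only two distinct analyses.
- If fewer than 5% of randomized subjects were affected by COVID-19, section 4.1.3.2 replaces the safety table with a listing. A listing of users still needs a rule for who is a user.
- The protocol's reason for tracking these drugs is interference with the immune response, and the two immunogenicity analyses agree with each other. The affected output is the least consequential of the three.
- Remote users may be few in the data, because earlier use did not have to be recorded.

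These points keep the matter small. None of them reconciles the two items.

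**Conclusion.** The concern holds. The current SAP defines pre-enrollment use of the same drugs by opposite windows in two parallel analyses, and neither document reconciles them. The harm depends on the literal wording having been followed: recent pre-enrollment-only users would then drop out of the exposed safety group, and remote users would enter it. The number of subjects cannot be stated. Only one exploratory, descriptive safety output is touched; the primary non-inferiority tests, the secondary test against 95% and the analysis-set definitions are unaffected. Severity is minor, and confidence that the text conflicts is high.

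**What to change.** In the SafAS item of SAP section 4.1.3.2, replace *at least 2 months* with *not over 2 months*, so that it matches the FASI item, the PPAS item, the exception note and the Table 4.5 footnote. State in the study report which rule was programmed, and rerun the safety table or listing if it was the literal one.

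The cost is one phrase and, at most, one exploratory output. No new data are needed, since medication start and stop dates are collected. According to the SAP version history, v1.1 was issued after the first database lock and the unblinding of the active phase, so the change should be labelled as a post-unblinding clarification. Version 1.1 was itself a text correction made at that stage.

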4.1.3.3 Safety overview analysis for subjects who had 5 doses

Because of study hold due to SAE and COVID-19, a proportion of subjects didn't complete the full vaccination schedule. To evaluate the safety events for subjects who had 5 doses, summary of safety overview will be performed on subjects who had 5 doses without consider time window.

4.2 Analysis Set

4.2.1 Full Analysis Set

The Full Analysis Set (FAS) is defined as the subset of randomized subjects who received at least 1 dose of the study vaccines.

The FASI is defined as a subset of the FAS, defined as all subjects from FAS who have a baseline RVNA titer lower than 0.5 IU/mL.

The analysis of immunogenicity addresses endpoints involving pre- and post-injection titers. The analysis will include all available data for each time point.

4.2.2 Per-Protocol Analysis Set

The PPAS is a subset of the FAS.

As D28 is the timepoint used for primary objective assessment, the PPAS will be defined at D28 (V05). The subjects presenting with at least one of the following relevant protocol deviations before D28 (ie, 14 days after the fourth vaccine injection) will be excluded from the PPAS:

- Subject did not meet all protocol-specified inclusion criteria or met at least one of the protocol-specified exclusion criteria
- Subject did not receive the first 4 doses of the vaccination schedule
- Subject received a vaccine other than the one that he / she was randomized to receive
- Preparation and / or administration of vaccine and concomitant medication (including HRIG for groups 1 to 3) was not done as per-protocol for the first 4 vaccinations
- Subject did not receive the first 4 vaccine injections in the proper time window
 - Vaccination 2 in [D03-D05]
 - Vaccination 3 in [D07-D09]
 - Vaccination 4 in [D13-D16]
- Subject did not provide the post-Dose 4 serology sample at V05 in the proper time window [D25-D31] from D0

- Subject received a protocol-prohibited therapy/medication/vaccine (belonging to categories 2 and 3) before V05
- Subject's serology sample is missing or did not produce valid test results at D0 or D28
- Seropositive subject at D0, ie, RVNA titer \geq LLOQ
- Subject developed a protocol-specified withdrawal criterion during the study but was not withdrawn
- Subject did not receive the correct amount of HRIG at D0

Adherence to the definition of the PPAS analysis set may also be decided during the blinded data review, ie, before breaking the code and locking the database.

4.2.3 Safety Analysis Set

The SafAS is defined for each dose as the subset of subjects having received this dose. All subjects will have their safety analyzed after each dose according to the study vaccine they actually received and after any dose according to the study vaccines received at the first dose.

Safety data recorded for a vaccine received out of the protocol design will be excluded from the analysis (and listed separately). Thus, if a subject does not receive any study vaccine at a given visit or if the study vaccine received does not correspond to any protocol group at a specific dose, the subject is excluded from the SafAS at this dose; however, the subject will be included in the analysis for all doses combined (referred to as analysis "after any dose") according to the first dose received that corresponds to a protocol group.

Note:

- If one subject received both VRVg-2 vaccine and HRIG at first dose, the vaccination group for safety analysis is Group 1;
- If one subject received Verorab vaccine or Imovax Rabies vaccine at first dose, no matter HRIG was concomitantly administered or not, the vaccination group for safety analysis is Group 2 or Group 3;
- If one subject received VRVg-2 vaccine only at first dose, the vaccination group for safety analysis is Group 4;
- If one subject received HRIG only at first dose, the vaccination group for safety analysis is "Other" and will be excluded from safety analysis.

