12.2.2 Safety Analysis Set

The Safety Analysis Set (SafAS) is defined for each dose as the subset of subjects having received this dose. All subjects will have their safety analyzed after each dose according to the vaccine they actually received and after any dose according to the vaccine received at the first dose.

Safety data recorded for a vaccine received out of the protocol design will be excluded from the analysis (and listed separately). Thus, if a subject does not receive any vaccine at a given visit or if the vaccine received does not correspond to any protocol group at a specific dose, the subject is excluded from the SafAS at this dose; however, the subject will be included in the analysis for all doses combined (referred to as analysis “after any dose”) according to the first dose received that corresponds to a protocol group.

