3.3 Derived Endpoints: Calculation Methods

3.3.1 Safety

Terms used in the standard safety tables to describe the safety events are specified below.

- AE: Adverse event includes solicited reaction and unsolicited event (including non-serious and serious adverse events).
- Adverse Reaction (AR): Corresponds to AE related to the study vaccine (investigational product), unless otherwise specified.
- Immediate: Unsolicited systemic AE checked “Yes” in the field of “immediate (within 30 minutes from the vaccination)” by the Investigator in the electronic case report form (eCRF).
- Solicited reaction: Event pre-listed in the eCRF, and which occurred during the solicited period (up to 7 days after the day of each vaccination).
- Unsolicited AE: AE recorded in the eCRF as unsolicited systemic event or unsolicited injection site reaction.
- Unsolicited injection site reactions are to be considered as related to the study vaccine injection and therefore will be analyzed as ARs.

Note: HRIG being an additional study medication (non-investigational product), any AEs occurring at HRIG injection location will be reported as unsolicited systemic events in this study.

- Unsolicited AEs will be analyzed up to 28 days after any and each vaccination. Unsolicited AEs occurring before or after the defined period will not be presented in the summary for unsolicited AEs but will be presented in a separate listing. The exceptions are SAEs and AESIs which are unsolicited AEs collected during the whole study period (after the first vaccination to end of 6 months safety follow-up period).
- SAE: Unsolicited AE considered serious by the Investigator (reconciled with Global Pharmacovigilance database).
- AESI: Is one of scientific and medical concern specific to the Sponsor's product or program, for which ongoing monitoring and rapid communication by the Investigator to the Sponsor can be appropriate. The Medical Dictionary for Regulatory Activities (MedDRA) preferred terms (PT) defined in the protocol are:
 - Anaphylactic reaction (PT)
 - Encephalitis (PT)
 - Convulsion (PT)

3.3.1.1 **Solicited Reactions**

3.3.1.1.1 **Daily Intensity**

All daily records for solicited reactions will be derived into daily intensity according to the following classification: None, Grade 1, Grade 2, Grade 3, or Missing (Unknown).

For the derivation of daily intensity, the following sequential steps will be applied:

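### The SAP 4.2.3 Note excludes a subject given HRIG only at the first dose from safety analysis without limiting this to dose 1, contradicting the general any-dose rule for a subject vaccinated later

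*SAP*

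**What the plan says.** SAP 4.2.3 defines the Safety Analysis Set dose by dose, by receipt of that dose. Its second paragraph deals with a missed vaccination: "if a subject does not receive any study vaccine at a given visit", the subject leaves the set at that dose; "however, the subject will be included in the analysis for all doses combined", with the group assigned "according to the first dose received that corresponds to a protocol group".

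Protocol 12.2.2 has the same rule, with the trigger worded "if a subject does not receive any vaccine at a given visit". It makes no exception for HRIG.

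The SAP then adds a Note that the protocol does not have. Its first three bullets assign the group from what was given at the first dose:
- VRVg-2 with HRIG is Group 1.
- Verorab or Imovax Rabies, with or without HRIG, is Group 2 or 3.
- VRVg-2 alone is Group 4.

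The fourth bullet reads "If one subject received HRIG only at first dose, the vaccination group for safety analysis is" Other, "and will be excluded from safety analysis".

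SAP 3.3.1 describes the immunoglobulin as follows: "HRIG being an additional study medication (non-investigational product". HRIG alone at D0 is therefore a visit without a study vaccine, which is the situation the second paragraph covers.

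**The concern.** Take a subject who receives HRIG but no vaccine at D0 and then a study vaccine at a later visit. The second paragraph of SAP 4.2.3 keeps this subject in the any-dose analysis. The fourth bullet of the Note, a few lines below, removes the subject. A programmer cannot follow both.

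The safety description, including the SAE and AESI tables, is run on the Safety Analysis Set (SAP 4.1.2.2 and Table 4.5). If the bullet is followed, a subject exposed to HRIG and up to four vaccine doses contributes neither to numerators nor to denominators after vaccination. The same subject remains in the Full Analysis Set, the "subset of randomized subjects who received at least 1 dose of the study vaccines". That set serves immunogenicity, so this does not settle the safety question, but it does show that the subject counts as vaccinated elsewhere in the plan.

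**Working it through.** The plan states no figure on this point, so there is none to reproduce. The check has two parts: apply each rule to the possible cases, then size the effect.

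**Rules applied to cases**

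| Received at D0 | Received later | General rule (SAP 4.2.3 second paragraph; protocol 12.2.2) | Note, fourth bullet |
|---|---|---|---|
| HRIG only | No vaccine | Not in the set | Excluded |
| HRIG only | VRVg-2 at D3 and after | In any-dose analysis, under VRVg-2 | Excluded |
| HRIG only | One Verorab dose | In any-dose analysis, under Verorab | Excluded |
| Neither HRIG nor vaccine | VRVg-2 at D3 | In any-dose analysis, under VRVg-2 | Does not apply |

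The rules agree in the first row and conflict in the second and third. In those two rows the bullet also conflicts with the dose-by-dose definition for each later dose actually received.

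**Other text bearing on the conflict**

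- SAP 4.1.2.2 sets the any-dose denominator for unsolicited events as everyone with one or more vaccinations. That fits the general rule, not the bullet.
- SAP 4.7 declares no departure from the protocol on this point.

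**Size**

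Inputs: planned group sizes of 318 (Group 1) and 106 (each other group), from protocol Table 5.1 and SAP Table 2.1. The number of affected subjects, k, is not in the documents. I assume k = 1 to 3 and take the planned sizes as the any-dose denominators.

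- Share of the denominator, k/n. For n = 318: 1/318 = 0.31% to 3/318 = 0.94%. For n = 106: 1/106 = 0.94% to 3/106 = 2.83%.
- Change in a rate when one subject with the event is removed from x events in n: x/n − (x − 1)/(n − 1) = (n − x)/[n(n − 1)]. This is largest at x = 1, where it equals 1/n, that is 0.31 points for 318 and 0.94 points for 106.
- Largest case, where the removed subject had the only event of a type, with Clopper-Pearson 95% upper limits:
  - Group of 318: 1/318 = 0.31% (upper limit 1.74%) becomes 0/317 (upper limit 1.16%).
  - Group of 106: 1/106 = 0.94% (upper limit 5.14%) becomes 0/105 (upper limit 3.45%).

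**The case against.** The strongest reply is that the texts can be read together. The bullet could mean exclusion at dose 1 only, or only subjects who never receive a vaccine, or it could be a deliberate exception because HRIG alone matches none of the four groups. The first two readings would remove the conflict, but the bullet states neither limit, and its three companions use the same phrase for the subject's overall safety group. A deliberate exception is not labelled as one and would be an undeclared departure from protocol 12.2.2.

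The reply that the case is remote stands. Protocol 5.1.4 gives the vaccine (step 11) before HRIG (step 12) at V01, and protocol 5.2.10 lists a missed injection as significant non-compliance. Nothing in the documents shows that such a subject existed.

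A reader might infer more than the text supports, in three ways:

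- *That the bullet loses every event of such a subject.* SAP 3.3.1.2.4 already keeps unsolicited events before the first vaccination out of the analysis and lists them separately, and the SAE and AESI periods in SAP 4.1.2.2 start at first vaccination. Events between HRIG and the first vaccine are outside the analysis under either rule.
- *That serious events would go unseen.* Protocol 10.1 requires SAEs to be reported within 24 hours, and protocol 11.2 reconciles the pharmacovigilance and clinical databases. Only the summary tables are affected.
- *That only Groups 1 to 3 can be affected.* That describes planned treatment. The Note concerns treatment received, and HRIG given in error to a Group 4 subject is possible.

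**Conclusion.** The inconsistency is real and minor. For a subject given HRIG only at D0 and vaccinated later, the fourth bullet contradicts the general rule in its own section, protocol 12.2.2 and the any-dose denominator in SAP 4.1.2.2. Followed literally, it removes that subject's post-vaccination AEs, SAEs and AESIs from the summary tables.

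One such subject shifts a rate by at most 0.31 points in Group 1 or 0.94 points in a group of 106. These figures assume planned group sizes and at least one affected subject; the true number may be zero. The non-inferiority analysis, the test against 95% and the sample size are unaffected.

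A related gap remains even if the bullet is dropped. The general rule does not say whether HRIG at D0 followed by VRVg-2 at a later visit is Group 1 (VRVg-2 with HRIG) or Group 4 (VRVg-2 alone), because neither matches what was given at a single visit.

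**What to change.** Revise the fourth bullet of the SAP 4.2.3 Note so that:

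1. Exclusion applies to the dose-1 set, and to subjects who never receive a study vaccine; the latter are listed separately.
2. A subject vaccinated later is included after each later dose received, after any dose, and in the SAE and AESI tables, under the general rule (the first dose that matches a protocol group).
3. The SAP fixes, without reference to outcomes, whether HRIG at D0 followed by later VRVg-2 counts as Group 1 or Group 4.
4. Events between HRIG and the first vaccination are listed separately for these subjects.

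The report should also give the number of subjects classed as Other. If it is zero, no table changes. The cost is a few lines in the SAP and, if any subject is affected, a rerun of the safety tables concerned. No new data are needed.
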